In addition, attractive and informative packaging plays a crucial role in building a brand name (Keller KL, 2005). Studies have shown that recognized and reputable brand names are associated with increased consumer acceptance and adherence compared to generic drugs (Rafael GB et al, 2019; Faasse K, et al, 2013; Faasse K, et al, 2016). Thus, understanding women's and their partners' preferences regarding packaging design can help create a brand for antenatal MMS that is delivered through the national health system that promotes optimal use throughout pregnancy.

2. Study aims and objectives

This study aims to assess the relevance, acceptability, and utility of three interventions in supporting adherence to the MMS regimen of one tablet per day. The overall aims of the study are to:

1. Learn what pregnant women prefer regarding visual reminders and motivational messages to help them remember to take their MMS.
2. Identify challenges and supports that affect whether women can take their MMS daily throughout their pregnancy.
3. Work with end users (pregnant women) to design motivational messages and visual reminders that are culturally appropriate and relevant for the local community. These will be designed to help women consistently take one MMS tablet each day for the entire 180 days of their pregnancy.
4. To collect feedback from pregnant women and their partners regarding the packaging design for antenatal MMS delivered through the national health system. This feedback will be used to help finalize the MMS packaging design, including the color scheme, logo, brand name, and packaging features.

3. Study design

This is a longitudinal mixed-method study that uses a cross-over TIPS design. All enrolled pregnant women will be asked to take MMS for the duration of their pregnancy and will experience all three interventions in a specific order. In this way, everyone gets to experience each approach. The women will receive exposure to each intervention for 3-4 weeks. On approximately the fourth week, eighth week, and twelfth week of the study, the pregnant women will be asked to participate in a focus group discussion (FGD) with other women in the province who also received the same intervention the previous weeks. This process will be iterated in the same way for Intervention A, Intervention B, and Intervention C.

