At the end of the study, in week 13 or 14, after having experienced all three adherence interventions, women in the TIPS study and their husbands/partners will be invited to a participatory workshop to discuss their preferences for the MMS product packaging.

The interventions are described below.

Intervention A: MMS + Family Support

- This intervention focuses on leveraging the power of a pregnant woman's social support network.
- Participants will receive 180 tablets of MMS and be asked to take MMS for the duration of her pregnancy.
- Additionally, study team members will work with participants to enlist the support of family members (spouse, mother-in-law, sister-in-law, etc.).
- Family members will be invited to a 1-hour orientation meeting to discuss the benefits of MMS for pregnant women and babies. They will be encouraged to provide daily encouragement and reminders to help the pregnant woman stay on track with her MMS regimen.
- Family members will be provided with an illustrative list of messages that could help encourage and motivate the women to take the MMS daily.
- This approach aims to harness the family's positive influence in promoting medication adherence.

Intervention B: MMS + Visual Reminders

- This intervention emphasizes the use of visual cues to support medication adherence.
- Participants will receive 180 tablets of MMS and be asked to take MMS for the duration of her pregnancy.
- They will also be provided with wall calendars specifically designed for the TIPS program.
- These calendars will likely include:
 - Designated spaces to mark MMS intake days.
 - Educational information about MMS and its benefits for maternal health.
 - Motivational messages to encourage consistent medication use.
 - Additional health information relevant to each trimester of pregnancy.
- By having a visual reminder readily available, participants can easily track their MMS intake and stay motivated throughout the program.

Intervention C: MMS + Social Media Posts and Videos

- This intervention utilizes a social media approach to encourage adherence.
- Participants will receive 180 tablets of MMS.
- They will also be exposed to educational and motivational messages delivered by healthcare providers through social media videos and social media posts.
- These social media posts and videos will be posted on various social media platforms (Facebook, Tik Tok) and participants will be sent links to their emails and phones and asked to watch them.

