9-11	C	Same women	Same women	Same women	Same women	
12	Focus Group Discussions					
Total		12-15	12-15	12-15	12-15	48-60

The study participants will include approximately 48-60 pregnant women attending their first ANC in their first trimester at a public health center. Approximately 48-60 pregnant women will be recruited across 4 health centers in Kampong Chhnang, Rattanakiri, Takeo, and Kampot. It is estimated that approximately 12-15 pregnant women will be enrolled per province. Pregnant women will be purposively recruited at their **first antenatal care visit** (~8-14 weeks gestation). An attempt will be made to select women of diverse sociodemographic characteristics.

For the participatory workshops to co-design the MMS package, we plan to invite all women and their husbands enrolled in the TIPS study design. The first 25 from each province who agree to participate will be registered to attend the participatory workshop. We will aim to have a relatively equal proportion of men and women.

6a. Inclusion criteria for pregnant women

- Age 18-45 years
- Attending first ANC
- Low-risk pregnancy, which includes being pregnant with a single pregnancy and the absence of any other medical or surgical conditions
- Reside in Kampong Chhnang, Rattanakiri, Takeo, and Kampot and not planning to move away within four months
- Agree to try to take MMS as their prenatal supplement
- Agree to participate in three FGDs, one every three months
- Agree to bring MMS bottles to the FGD each month for tablet counting

6b. Exclusion criteria for pregnant women

- Pregnant women who do not fall into the age range of 18-45
- Came to the health facility after first ANC
- Midwives and/or doctors have classified pregnant women as having a high-risk pregnancy.

6c. Inclusion criteria for husbands

- Willingness to participate in the participatory workshop
- Confirmed availability for date and time of workshop

6d. Exclusion criteria for husbands

- Unwillingness to participate in the participatory workshop
- Did not confirm availability for the date and time of workshop

6e. Recruitment process and taking informed consent

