Selected healthcare providers (e.g. midwives, doctors) from the primary health center will attend an orientation and training on the objectives and design of the study, the benefits of IFA or MMS supplementation during pregnancy, and any expected risks with participation. Healthcare providers will be trained on the protocol for enrollment (e.g., inclusion and exclusion criteria), obtaining verbal consent, and recording registration data. A primary healthcare worker in the health center (receiving an incentive payment from the study) will invite pregnant women to participate, give an overview of the study, including any risks, and ensure they meet all inclusion criteria. Healthcare workers will obtain verbal informed consent, provide the MMS-180, and explain that the study team will contact the participants within 72 hours and visit them in their homes to obtain written informed consent. If the woman agrees, she will provide her contact number, which the healthcare worker will submit to the study team by the end of the day. The women will then receive MMS-180 and be counseled on its use. A member of the study team will reach out to the new participant ideally within 72 hours to confirm participation, informed consent, and that the woman received the supplements. Up to two weeks will be allowed from the time of verbal informed consent at the health center until written consent is obtained at the participant's home. A record of all women screened but not enrolled will be maintained. The enrollment form is included in Annex A and the informed consent form for TIPS is included in Annex B. The informed consent form for the participatory workshop is in Annex C.

7. Study procedures

In each of the four health centers, a designated healthcare provider will enroll up to 15 pregnant women with first ANC visit. All women will receive all three interventions (family support, wall calendars, social media posts and videos) sequentially over 12 weeks. Women will be exposed to each intervention for 3-4 weeks, followed by a FGD to share their experiences and feedback. This iterative process helps researchers improve the interventions for better MMS adherence during pregnancy.

7a. Participant allocation

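### Aim 2 covers MMS intake for the whole of pregnancy, but adherence and barrier data stop at about week 12, roughly half-way through the 180 tablets

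*Combined protocol and SAP*

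**What the plan says.** Section 2 gives Aim 2 as: "Identify challenges and supports that affect whether women can take their MMS daily throughout their pregnancy". Aim 3 concerns the messages and reminders to be produced: "These will be designed to help women consistently take one MMS tablet each day for the entire 180 days of their pregnancy". Section 3 adds that "All enrolled pregnant women will be asked to take MMS for the duration of their pregnancy".

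The schedule is shorter:

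- Section 6 places entry at the first antenatal visit, at about "8-14 weeks gestation". The 180 tablets are handed over there (section 6e).
- Section 7 states: "All women will receive all three interventions (family support, wall calendars, social media posts and videos) sequentially over 12 weeks".
- Section 3 times the focus groups: "On approximately the fourth week, eighth week, and twelfth week of the study".
- Tablets are counted at the focus groups (section 7f), and the adherence period runs from the date the tablets were received to the date of the focus group (section 10b).
- The study ends in week 13 or 14 with a packaging workshop (sections 3 and 7e). No tablet count or discussion of barriers is planned there, and nothing is scheduled afterwards.
- Section 7c asks families to keep up their reminders until the 180 tablets are used, but no data are planned for that later period.

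One inclusion criterion in section 6a spaces the three focus groups three months apart. The next criterion has women bring their bottles monthly.

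**The concern.** Aim 2 is a research aim whose stated scope is the whole pregnancy. The data that could answer it come only from the focus groups and the tablet counts made there, and both end at about week 12. What helps or hinders intake after that point is not recorded, and no analysis can recover it.

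The barriers may well change. The protocol's own background reports that pregnancy-related experiences such as nausea and fatigue, along with forgetfulness, went with low adherence in the earlier Cambodian trial. How such experiences affect intake late in pregnancy would not be observed here. Each cue is also tried for only 3-4 weeks, so the data say little about whether it still works months later.

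The study is meant to shape practice before wider introduction. If it is reported against Aim 2 as worded, barriers and supports from early use would be presented as those of the whole pregnancy.

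**Working it through.** No test or power calculation is involved; this is calendar arithmetic.

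**Inputs**

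- Gestation at entry: 8-14 weeks (section 6).
- Last focus group and tablet count: about week 12 (sections 3, 6 and 7c).
- Last contact of any kind: week 13 or 14 (section 3).
- Tablets supplied: 180, one a day (sections 2 and 3).
- Time allowed from verbal to written consent: up to 2 weeks, with tablets already in hand (section 6e).
- Wait from first antenatal visit to study week 1: not stated. A 4-week wait is my assumption, to show sensitivity.
- Start of the third trimester: not defined in the documents. I assume 28 weeks.

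**The plan's own figure.** Three cycles of 3 weeks' exposure plus 1 focus-group week: 3 x (3 + 1) = 12 weeks. This reproduces the stated 12 weeks.

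**Coverage at the last tablet count**

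Tablet-days covered = 7 x (12 + wait). Gestation = entry gestation + 12 + wait.

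| Wait | Tablet-days covered | Not observed | Gestation at last count |
|---|---|---|---|
| 0 weeks | 7 x 12 = 84 (84/180 = 47%) | 96 (53%) | 8 + 12 = 20 to 14 + 12 = 26 |
| 2 weeks (consent limit) | 7 x 14 = 98 (98/180 = 54%) | 82 (46%) | 22 to 28 |
| 4 weeks (assumed) | 7 x 16 = 112 (112/180 = 62%) | 68 (38%) | 24 to 30 |

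The tablet-day share depends only on the time since the tablets were received, not on gestation at entry.

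**Where the regimen would end.** 180/7 = 25.7 weeks, so one tablet a day runs to 8 + 25.7 = 33.7 weeks for the earliest entrants and 14 + 25.7 = 39.7 weeks for the latest. For the week-12 count to cover all 180 days, the wait before week 1 would have to be 25.7 - 12 = 13.7 weeks, far beyond anything the plan describes.

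**Third trimester.** With a 28-week start, the last count falls at or before that point for waits of up to 2 weeks. With the assumed 4-week wait, the latest entrants contribute 30 - 28 = 2 weeks.

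**The three-monthly criterion read literally.** At about 13 weeks apart, the focus groups would fall at about 21, 34 and 47 weeks for a woman entering at 8 weeks, and at about 27, 40 and 53 weeks for one entering at 14. The third would come after delivery. This reading also contradicts the week 4, 8 and 12 schedule and the monthly bottle criterion, so it cannot be relied on to supply late-pregnancy data.

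**The case against.** The strongest reply is that this is small formative research. A short trial of candidate cues suits that purpose, the overall aim statement in section 2 sets no 180-day horizon for assessment, and section 10b plans only descriptive counts without tests. That stands. It supports low severity and a change of wording, not a redesign. It does not make the scope of Aim 2 match the data.

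Several stronger readings are tempting, and the documents do not support them:

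- *Aim 3 promises to measure 180-day adherence.* It does not. It states what the materials are for, namely to help women "consistently take one MMS tablet each day for the entire 180 days of their pregnancy". What remains is that the materials will be untested for the later part of their intended use.
- *The plan will draw a conclusion about 180-day adherence.* No section states one.
- *The whole third trimester goes unstudied.* This depends on an assumed 28-week start and on a wait before week 1 that the plan leaves undefined. The entry range is approximate, and the criteria in sections 6a and 6b set no explicit gestational limit. The supportable statement is most of the third trimester.
- *The calendar's late-pregnancy content goes unexamined.* Section 3 says calendars will probably carry "Additional health information relevant to each trimester of pregnancy", but nothing says they are withdrawn after week 8. Section 3 has the discussions compare interventions, and women can comment on later content in advance.

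Women can also be asked about barriers they expect later. Such answers are useful, but they are anticipated rather than experienced barriers.

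**Conclusion.** The concern holds for Aim 2, at low severity. Its scope is the whole pregnancy, while the planned data describe about the first 12 weeks of use.

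The tablet-day coverage of 47-54% assumes that study week 1 follows tablet receipt within the two-week consent limit; a longer wait raises it, as the working shows. The gestation figures also rest on entry at about 8-14 weeks, and the statement about the third trimester on an assumed 28-week start. None of these assumptions, varied within the ranges shown, brings the observation period close to the full regimen.

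A reader might infer that the design cannot serve its formative purpose, or that Aim 3 is equally at fault. Neither follows. Aim 3 can stay as it is, and early-use findings remain informative if they are labelled as such.

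**What to change.** 1. Reword Aim 2, and any conclusion drawn from it, to challenges and supports during about the first 12 weeks of MMS use (to about 20-28 weeks of gestation). State that adherence and barriers over the full 180 days are not assessed. The only cost is a narrower claim.
2. Reconcile the three-monthly focus-group criterion in section 6a with the week 4, 8 and 12 schedule and the monthly bottle criterion. This is a text correction.
3. Optional, if the sponsor wants to keep the full-pregnancy wording: add one short late-pregnancy phone contact, using the numbers already collected. It would ask how many tablets remain, which cues are still in use and what barriers have arisen since week 12. The cost is about 48-60 calls, a line in the consent form and a later end date. The limits should be stated: answers are self-reported, they cannot show which cue helped because all three will have been introduced, and some women may have delivered if the call is left to day 180.

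No sample size figure changes.

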For the TIPS, the sample size of 48-60 women (around 12-15 women per province) is purposive but has been selected for two reasons. First, the sample size of 12-15 women per province allows enough women to participate in a FGD. Considering that an ideal number for FGD is 8-10 people if 20% of the participants are expected not to show, there would still be enough participants to conduct an FGD. Second, based on previous formative research with pregnant women in Kampong Thom, there was not much variation in the experiences of women regarding MMS acceptability and their perceptions of the benefits of various strategies to improve adherence. Thus, one FGD per province is believed to be sufficient to capture the range of perspectives on the different interventions and achieve saturation, or the point at which no new significant themes or insights emerge from the data.

For the participatory workshops to design the MMS product package, approximately 100 participants will be recruited across four provinces in Cambodia (25 participants per workshop, 4 workshops total). Participants will be pregnant women who have previously participated in the TIPS program and their husbands/partners. The sample size is a convenience sample and chosen for the following reasons. First, it is anticipated that with a focused group like pregnant women and their partners who have a shared experience with the TIPS program, 25 per province is likely enough to reach saturation. Second, the study must consider logistical manageability and group dynamics. With 25 participants, workshops can maintain a manageable size for group discussions and activities. This allows for active participation, ensures everyone has a chance to be heard, and facilitates effective interaction. Thirdly, smaller workshops require fewer facilitators, materials, and space, making them more cost-effective and easier to organize across four different provinces.

6. Participant recruitment and selection

The research team will aim to recruit 12-15 pregnant women attending their first ANC per province. Ideally, from 8-10 of these women will then join the FGD to discuss their experiences with that specific intervention (see Table 1).

Figure 1. TIPS sample size per province

Week	Interventions	Kampong Chhnang	Rattanakiri	Takeo	Kampot	Total
1-3	A	12-15	12-15	12-15	12-15	48-60
4	Focus Group Discussions					
5-7	B	Same women	Same women	Same women	Same women	
8	Focus Group Discussions					

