Recruitment and scheduling: In each province, all pregnant women who have completed the specific intervention period (e.g., all used wall calendars for 3-4 weeks) will be invited to participate in an FGD. The research team will schedule a convenient time for a 70-minute discussion in a convenient, private, comfortable location.

Moderator and notetaker: The research team will identify a trained moderator familiar with MMS and the project's interventions. Additionally, the research team will identify a trained notetaker present to capture key points and nonverbal cues.

Discussion Guide: The research team will use the intervention-specific semi-structured discussion guide(s) with open-ended questions for each intervention (See Annex D for a discussion guide for Intervention A; Annex E for a Discussion guide for Intervention B; and Annex E for a Discussion guide for Intervention F). For each intervention, explore the following themes:

- Acceptability of the intervention (e.g., ease of use, cultural appropriateness)
- Explore fit-for-purpose, such as the intervention's ability to support adherence to MMS during the intervention period.
- Perceived pros and cons of the intervention
- Suggestions for improvement

Conduct of the FGD: Start with introductions, explain the purpose of the discussion, and establish ground rules for respectful communication and confidentiality. Ensure informed written consent. Inform participants that the FGD will be audio-recorded. The moderator will guide the conversation using the discussion guide, ensuring all participants have a chance to share their experiences. Encourage open discussion and probing for details and insights. The moderator will practice active listening techniques, and the notetaker will capture key points, quotes, and nonverbal cues for later analysis.

7e. Conduct of participatory workshops

Recruitment process:

- All women who previously participated in the TIPS program within the targeted provinces will be contacted by phone. During the call, invite the woman's partner/husband to attend the workshop with her. Explain that their joint perspectives are valuable.
- Briefly explain the workshop purpose, eligibility criteria, and incentive.
- If interested, obtain verbal consent to participate and schedule the workshop.
- Confirm availability of the proposed date, time and location of workshop.

Pre-workshop preparation:

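### Can 25 people per packaging workshop be recruited from a pool of 12-15 women per province and their partners?

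*Combined protocol and SAP*

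**What the plan says.** Section 5 gives the workshop size: "approximately 100 participants will be recruited across four provinces in Cambodia (25 participants per workshop, 4 workshops total"). It then defines who may attend: "Participants will be pregnant women who have previously participated in the TIPS program and their husbands/partners". It calls this a convenience sample and gives three reasons for the number. One concerns saturation ("25 per province is likely enough to reach saturation"), one concerns group size ("With 25 participants, workshops can maintain a manageable size for group discussions and activities"), and the third concerns cost and ease of organisation.

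The size of the source group is set elsewhere. Section 6 says "It is estimated that approximately 12-15 pregnant women will be enrolled per province", and Section 7 sets a ceiling at each of the four health centers: "a designated healthcare provider will enroll up to 15 pregnant women with first ANC visit". On workshop recruitment, Section 6 invites all enrolled women and their husbands, aims for roughly equal numbers of men and women, and applies a registration rule: "The first 25 from each province who agree to participate will be registered to attend the participatory workshop". Section 7e describes the route: "All women who previously participated in the TIPS program within the targeted provinces will be contacted by phone", and the partner is invited in the same call. No other source of participants is named.

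**The concern.** The workshop sample comes from a closed group whose size the plan fixes in advance. Twelve women with one partner each make 24 people, so at the low end of planned enrolment the workshop cannot reach its stated size even if everybody attends. At higher enrolment, 25 is possible only if nearly all eligible women and partners agree.

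The plan allows for 20% non-attendance at the focus groups but states no allowance for the workshops. These come later, in week 13 or 14, and also need husbands to be available. On that reading, the plan promises a number it may well miss. An ordinary turnout in the low twenties could then look like under-recruitment, and the remark about saturation would be attached to a ceiling instead of the number likely to come.

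**Working it through.** **Inputs.** Workshop size 25 in each of 4 provinces (Section 5). Women per province 12 to 15 (Sections 5 and 6), with at most 15 per health center and four centers (Section 7). Eligible: these women and their husbands or partners (Sections 5, 6 and 7e). Assumption: one partner per woman and no withdrawals, which gives the largest possible pool.

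**The plan's own figure.** 25 × 4 = 100. The stated total is reproduced, so there is no multiplication error.

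**Pool and uptake needed.** Pool per province = 2 × women. Uptake needed = 25 / pool. Loss that still leaves 25 = (pool − 25) / pool.

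| Women per province | Pool | Pool, four provinces | Uptake needed for 25 | Loss that still leaves 25 |
|---|---|---|---|---|
| 12 | 24 | 96 | 25/24 = 104% (not possible) | none; one short |
| 13 | 26 | 104 | 25/26 = 96.2% | 1/26 = 3.8% |
| 14 | 28 | 112 | 25/28 = 89.3% | 3/28 = 10.7% |
| 15 | 30 | 120 | 25/30 = 83.3% | 5/30 = 16.7% |

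**Size of the strict conflict.** With full uptake and the cap of 25, a province contributes min(25, pool): 24 at 12 women and 25 at 13 to 15 women. If k of the four provinces enrol exactly 12, the total is 100 − k, so it lies between 96 and 100. The stated total is given only as approximate, and the enrolment range behind it is also worded as approximate.

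**Fit with the sex balance.** With equal numbers of men and women, 25 people are 25/2 = 12.5 couples, which lies inside the planned 12 to 15 women per province.

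**Sensitivity to turnout (assumed rates).** The plan gives no workshop turnout. Suppose people are lost independently before registration and attendance is capped at 25. The expected attendance is then:

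| Assumed loss | 12 women | 13 | 14 | 15 | Four provinces |
|---|---|---|---|---|---|
| 0% | 24 | 25 | 25 | 25 | 96 to 100 |
| 10% | 21.6 | 23.3 | 24.5 | 24.9 | 86 to 100 |
| 20% | 19.2 | 20.8 | 22.3 | 23.6 | 77 to 94 |

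The 20% row borrows the figure that Section 5 gives for the focus groups only. The expected number can thus fall well below 25, but only through a rate that the reader supplies.

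**What depends on 25.** The workshop outputs are votes on packaging elements and discussion themes. The plan specifies no hypothesis test, precision target, minimum workshop size or replacement rule for them. In Section 6 the number 25 works as a stopping point for registration, and in Section 5 the group-size and cost reasons are arguments for a maximum.

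**The case for a change.** The best case for a change is that the inconsistency is real and cheap to remove. Section 5 presents 25 as the number that will be obtained, yet at 12 women, a figure inside the plan's own range, it cannot be. The pool of 24 to 30 is also a best case, because women may withdraw and husbands must confirm that they are free. If the focus-group loss of 20% carried over, the chance that at least 25 people remain would be 0, 0.02, 0.16 and 0.43 at 12, 13, 14 and 15 women. Stating 25 as an upper limit would bring Section 5 into line with Section 6.

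The pool arithmetic stands, and so does the remark that Section 5 is phrased as a target while Section 6 operates a cap. The rest is weaker:

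- The turnout figures are assumptions, since the documents say nothing about workshop attendance in either direction.
- The fear that a smaller workshop would count as a shortfall has no basis in the plan, which defines no shortfall.
- The saturation argument calls 25 likely to be enough. That is a statement of sufficiency, and it does not imply that 22 would be too few.
- The rewording would leave recruitment, the cap and workshop conduct as they are.

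**Conclusion.** The concern is factually right but calls for no change. Assuming one partner per woman and no withdrawals, the stated workshop size exceeds the pool by one person in any province that enrols exactly 12 women, and so by at most four people in total (96 against about 100). At 13 to 15 women it can be reached, with uptake of 96% down to 83%. A gap of that size falls within the looseness the plan declares for both numbers.

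The study team has a workable rule in Section 6: invite everyone eligible and stop registering at 25. If fewer agree, the workshop runs with fewer, and the descriptive summaries are reported on those who attended. Nothing inferential rests on the count. This is a small mismatch of wording between two sections, and correcting it would bring no gain in conduct, analysis or interpretation.
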